 - Booster sessions will include a review of the RRP, identification and reinforcement of accomplishments, as well as identification of and problem solving around any social barriers to the RRP.
 - The RRP will be revised based on identified accomplishments and social barriers at each booster session.
 - **Control Intervention**
 - Participants randomized to the time-attention matched control condition will participate in a relaxation and stress reduction intervention that also consists of two one-hour sessions held one week apart and two brief 20-30 minute booster sessions held two- and four-weeks after the 2nd hour long session.
 - Content will serve to keep the RA blind to participant condition and will include a series of guided relaxations (e.g., breathing meditation, visual imagery).
 - During booster sessions, the interventionist will review participants’ success with their relaxation plan and identify further strategies to integrate relaxation into daily lives.

Analysis

- At 2-time points during phase 3, compute descriptive data on all target outcomes in Table 1 and discuss how actual outcomes compare to target outcomes.
Discrepancies will result in: 1) investigation of the reason for failure to meet this outcome, and 2) discussion among the research team.

4.3 Measures (Phases 2 & 3) -- For the complete list of standardized measures administered at baseline and at follow up time points, refer to the Phase 3 RCT Measures document.

Acceptability:

- 8-item Client Satisfaction Questionnaire-Revised (CSQ-8-R) (Attkisson & Zwick, 1982) will be used to assess satisfaction with the intervention.
- An End of Intervention Questionnaire (EIQ) will be developed that will assess the perceived helpfulness of intervention components.
- These scales will be administered to both conditions after the initial 90-min intervention (PI), as well as after each booster session.
- Exit interviews will be conducted with participants randomized to the STARS intervention.

Primary Outcomes:

(1) **Composite Risk for HIV (CR-HIV)** is a binary indicator of any HIV risk (e.g., yes=1 vs. no=0), which is an algorithm based on whether the participant:

- report condomless anal sex with a HIV serodiscordant or status-unknown primary or other partner in the past 3 months;
- is using PrEP;
- is in a monogamous partnership with an HIV-uninfected partner or an ;
- is in a monogamous partnership with an HIV-infected partner who is virally suppressed.

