- If participants are not certain about the latter two indicators, they are coded as having HIV risk according to this algorithm.

(2) **IPV frequency** will be assessed with:

- The Composite Abuse Scale revised short form (CASr-SF).and
- A trans-specific IPV Scale (T-IPV Scale; Peitzmeier et al, in press) that assesses IPV unique to TW (e.g., being forced not pursuing aspects of gender transition that you wanted).

(3) **IPV safety** will be assessed with the:

- Measure Of Victim Empowerment Related to Safety (MOVERS; Goodman et al., 2015), which is a 13-item scale that measures IPV survivors' safety-related psychosocial skills and efficacy and expectations of support, as well as the extent to which survivors feel that their efforts to achieve safety might create new difficulties.

Secondary Outcomes:

- **Biologically determined STI diagnoses, including HIV** - The research staff will work with participants to find gender-affirming health care clinics in their area that provide free or low-cost STI and HIV testing. Participants will be encouraged to get tested for STIs as part of the research

study; however, STI testing is not a requirement for participation. HIV self-test kits will be mailed to willing participants and the research staff will walk participants through testing procedures as well as post-test result counseling (as needed) over Zoom or in-person.

- Self-reported discrete **behavioral risk indicators**: CAS, multiple and concurrent partnerships, partners' HIV status, monogamy and sexual agreements, substance use including injection drug use, HIV testing behaviors (including self-testing) and knowledge, intentions to use PrEP, PrEP uptake, use of any HIV prevention services, and use of any additional IPV-related services/resources.

Exploratory Tertiary Outcome/Potential Mediators: Refer to the Phase 3 RCT Measures document for the complete list of standardized measures administered at baseline and at follow up time points.

5. Dissemination

- Throughout the study, we will disseminate process reports and descriptive summaries of the findings to colleagues at social service and medical/health agencies with whom we established MOUs.
- As data are evaluated, we will prepare brief reports describing the major findings from the study which we will share with our community partners, HIV prevention and IPV scientists, and TW health and advocacy organizations through publications and presentations at professional conferences.

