HIV Risk Reduction Intervention for Transwomen with Intimate Partner Victimization:

Statistical Analysis Plan

Descriptive statistics will be used to characterize the study sample and compare baseline differences between intervention conditions. Fidelity to intervention protocols will be assessed using adherence and competence ratings on approximately 5% of all completed sessions, balanced across peer counselors and study. Feasibility will be quantified based on retention and attrition rates, which will be visualized in a CONSORT diagram.

To explore the preliminary efficacy of the intervention, mean values for key study outcomes (i.e., empowerment, IPV frequency, PTSD symptoms, depressive symptoms, and HIV vulnerability) will be plotted across study time points (baseline, post- intervention, 4-month, and 6-month follow-ups). We additionally will test for intervention effects using intent-to-treat models with all available data. Linear mixed models (LMMs) with maximum likelihood estimation will be used for continuous outcomes (e.g., empowerment, PTSD symptoms, and depressive symptoms). Count-based outcomes (e.g., past-2-month frequency of IPV, past-60-day number of HIV-vulnerable sex acts) will be dichotomized to indicate any vs. no occurrence (0 = none, 1 = any instance). These binary outcomes will be modeled using GLMMs with a binomial distribution and logit link function. All models will include fixed effects for condition, time, and condition \times time interactions. Any significant baseline demographic differences will be included as covariates in the final models. An unstructured covariance matrix will be used to account for within-participant correlations across time points.

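### IPV frequency is a primary outcome, but the SAP models it only as any versus none, so the trial gives no between-arm estimate or interval for frequency itself

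*SAP*

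**What the plan says.** Protocol section 4.3 (Primary Outcomes) names IPV frequency as the second primary outcome. It is measured by two instruments: "The Composite Abuse Scale revised short form" (CASr-SF) and a trans-specific scale (T-IPV) "that assesses IPV unique to TW". Neither document states how the two are combined or what response format they use; the protocol refers the reader to a separate measures document.

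The SAP gives "past-2-month frequency of IPV" as an example of a count-based outcome and states that such outcomes "will be dichotomized to indicate any vs. no occurrence (0 = none, 1 = any instance". It continues: "These binary outcomes will be modeled using GLMMs with a binomial distribution and logit link function". The models contain condition, time and their interaction, and "An unstructured covariance matrix will be used to account for within-participant correlations across time points".

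The only other use of IPV frequency in the SAP is descriptive: mean values "will be plotted across study time points". There is no count, ordinal or score model for IPV, no sensitivity analysis on the undichotomised measure, and no reason given for dichotomising.

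**The concern.** The outcome is named as a frequency, and the only modelled quantity is whether any IPV occurred in the window. A participant whose IPV falls from many incidents to one has the same value at that visit as one whose IPV did not change. A plot of means shows direction, but it is neither an estimate of a difference nor an interval.

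The Phase 3 procedures seek preliminary evidence that STARS improves the primary outcomes, and section 3 says the findings are groundwork for a large efficacy trial. What such a trial takes from a pilot is an estimate and its uncertainty. For this outcome the plan supplies them for prevalence of any IPV on an unnamed scale, and not for frequency.

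**Working it through.** **What the text settles.** Setting protocol section 4.3 beside the SAP, the named outcome is a frequency on two scales, the modelled outcome is any/none on an unspecified scale, and the remaining use is a plot. This part needs no assumption. The plan states no power, effect size or event rate for IPV, so there is no figure of its own to reproduce.

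**What the any/none odds ratio can see.** Assume negative binomial counts with mean m per 2 months and variance m + a·m².

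- With a = 1, P(any) = m/(1+m), so the odds of any IPV equal m. Halving m gives an odds ratio of exactly 0.50 at every mean. The share with any IPV moves from 14% to 8% (m = 1/6), 50% to 33% (m = 1) and 86% to 75% (m = 6).
- With a = 2, the odds are √(1+2m) − 1. Halving m gives (√1.167 − 1)/(√1.333 − 1) = 0.52 at m = 1/6 and (√7 − 1)/(√13 − 1) = 0.63 at m = 6.

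So the group odds do move with a partial reduction. They equal the rate ratio only under a particular distribution, which the trial would not know.

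**Precision at one visit, a = 1, 25 per arm** (1:1 allocation is assumed; the protocol says up to 50 in total). The variance contributed by each arm is (1/m + 1)/25 for the log rate, with dispersion treated as known. For the log odds of any IPV it is (1/m + 2 + m)/25. The any/none version is larger by (1 + m)/25, which is small at low means and large at high ones.

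| Mean, control vs STARS | SE, log rate ratio | SE, log odds ratio | Ratio |
|---|---|---|---|
| 1/6 vs 1/12 | √(20/25) = 0.894 | √(22.25/25) = 0.943 | 1.05 |
| 1 vs 0.5 | √(5/25) = 0.447 | √(8.5/25) = 0.583 | 1.30 |
| 3 vs 1.5 | √(3/25) = 0.346 | √(9.5/25) = 0.616 | 1.78 |
| 6 vs 3 | √(2.5/25) = 0.316 | √(13.5/25) = 0.735 | 2.32 |

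**Four-visit simulation.** Assumed: 25 per arm; visits kept at 100/90/80/70% (the last two follow the Table 1 retention targets, the 90% is assumed); total overdispersion 1 or 2; gamma or log-normal within-visit variation; constant effect from T2 to T4. The models were random-intercept negative binomial and random-intercept logit, with a 3-df likelihood-ratio test of condition × time and 1,000 data sets per setting (simulation error about 1.5 points). The SAP's unstructured covariance was not simulated.

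| Scenario | Count model, power | Any/none, power |
|---|---|---|
| Rate halved, mean 1/6 | 9-15% | 11-14% |
| Rate halved, mean 0.5 | 17-19% | 13-14% |
| Rate halved, mean 1 | 20-27% | 12-16% |
| Rate halved, mean 3 | 26-49% | 10-16% |
| Rate halved, mean 6 | 28-60% | 12-16% |
| IPV stops in 40% of STARS arm, mean 3 | 29-43% | 31-47% |
| IPV stops in 40% of STARS arm, mean 6 | 40-64% | 42-58% |

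These powers are not size-adjusted. Null rejection was 6.4-10.9% for the count model and 5.6-9.8% for the logit model.

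**Single-visit simulation**, rank test against any/none, 4,000 data sets per setting. Rate halved: 10-11% vs 14-15% at mean 1/6, equal at mean 0.5, and 25-61% vs 13-26% at mean 6. With 40% cessation at mean 6, any/none is better: 44-63% vs 59-90%. If counts are grouped as 0, 1-2, 3-5 and 6+ (overdispersion 1, rate halved), the figures are 12% vs 15%, 19% vs 19%, 25% vs 24%, 39% vs 21% and 42% vs 17% at means 1/6, 0.5, 1, 3 and 6.

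**What an added count model would deliver.** For a true 6-month rate ratio of 0.5, the typical 95% interval runs from 0.23-1.1 to 0.17-1.5 at mean 3 (0.5 divided and multiplied by 2.2 to 3.0). At mean 1 it runs from 0.16-1.6 to 0.12-2.0. At mean 1/6 it is about 0.03-7, which is uninformative.

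**The case against.** The best defence is that any/none is a sensible choice for sparse, skewed counts in at most 50 people. The study says it is mainly exploring patterns of results, and the SAP does plot mean frequency at all four time points. Even at mean 3, the typical added interval for a true halving includes 1. Most of this stands: it sets the stakes, and it is why the any/none model should stay. It does not supply the missing estimate, and the SAP does not itself give sparsity as its reason.

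Three stronger readings are tempting, and the documents do not support them.

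- *That any/none detects only cessation.* Any IPV in a 2-month window is not cessation, and its prevalence falls when rates fall, as the working shows. That a partial improver is scored as unchanged is true of the individual at that visit, not of the model's estimate.
- *That a substantial loss of power is established.* The clear advantage of a count model needs means of about 3 or more and a partial reduction. No 2-month IPV distribution is given. The entry criterion of one incident in 12 months might suggest a minimum of about 1/6 per 2 months. However, it is met on the CTS-2 or the T-IPV Scale, so it bounds neither the CASr-SF nor any follow-up visit.
- *That the sex-act count has the same mismatch.* Primary outcome (1), composite HIV risk, "is a binary indicator of any HIV risk" by the protocol's own definition, so this point does not extend to it.

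**Conclusion.** The point holds in limited form. From the text alone, a primary outcome named as a frequency on two scales will yield no between-arm estimate or interval for frequency, and the any/none model that stands in for it does not say which scale it uses.

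The size of the loss is unknown. On assumed distributions, any/none is less precise for a partial reduction at means of about 3 or more per 2 months, similar or slightly better at very low means, and about as good or better when IPV stops. The main gain from the change is therefore a direct estimate of frequency; added precision is conditional on facts the documents do not contain. In an exploratory pilot this is a worthwhile and inexpensive improvement. Nothing here makes the planned any/none analysis invalid.

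**What to change.** Keep the any/none GLMM, label it 'any IPV, past 2 months', and name the scale it uses or fit it for each scale. Then add to the SAP:

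> For CASr-SF and T-IPV separately, past-2-month IPV frequency will also be analysed in one exploratory mixed model with condition, time and condition × time, the same covariates as the any-IPV model, and a random participant intercept. This departs from the unstructured covariance used elsewhere. The model type follows the scale's response format and is recorded before outcome data are examined by arm: negative binomial with log link for counts, proportional odds for ordered categories. The rate ratio or common odds ratio with its 95% CI will be reported beside the any-IPV odds ratio for the same scale. If the model does not converge, this will be reported with descriptive frequencies by arm and visit, and no other model will be substituted.

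Cost: SAP wording and two exploratory models, with no new data if the scales record counts or frequency categories (the documents do not say).

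Downsides:

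- There are extra exploratory estimates to interpret.
- Intervals will be wide, and the model may not converge, if counts are low. At mean 1/6 with the rate halved, 58-63% of simulated data sets had an arm-visit with no IPV, where neither model gives a finite estimate. The any/none model has the converse difficulty at high counts: at mean 6, 7-68% of data sets had an arm-visit in which everyone or no one reported IPV.
- Tests are somewhat liberal at this sample size, so intervals should be read as descriptive.

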- (1) Develop a behavioral intervention manual that addresses the specific and unique HIV prevention needs of TW with IPV, and that uses a gender-affirmative, empowering, and trauma-informed approach**
- (2) Evaluate the feasibility, acceptability, safety, and initial effects of STARS through three phases of intervention development.**

We are primarily interested in exploring the pattern of results for any evidence of support for the intervention's influence on our primary and secondary outcomes.

Long-term aim: The findings from this R34 intervention development study will provide the groundwork to examine the efficacy of STARS in a future, large-scale clinical trial, which can be readily implemented in real-world settings.

4. Description of Study Design, Materials and Methods

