- Retention strategies: close communication and collaboration with CBOs that serve local TW and hiring an outreach specialist from within the local trans community.

Procedures

- Pilot STARS among TW ($n=5-8$) with elevated HIV risk and IPV.
- Elicit feedback via exit interviews (structured informant interview and evaluation surveys) to finalize STARS protocol and research procedures.
- Refine and finalize STARS manual, interventionist training protocol, and fidelity scales using participant feedback and acceptability and feasibility metrics.

Analysis

- Detailed notes of IDI exit interviews will be analyzed (consider recording) to review feedback and make final adjustments
- At the end of phase 2, compute descriptive data on all target outcomes in Table 1 and discuss how actual outcomes compare to target outcomes.
- Discrepancies will result in: 1) investigation of the reason for failure to meet this outcome, and 2) discussion among the research team.

[figure not shown]
Table 1. Target Outcomes	
Description (Assessment method)	Target
Feasibility and Acceptability— SAS, RT	
Acceptability (End of Intervention Survey; see C10.3)	Endorsing an average score of 3 or more (out of 5) for each rated intervention component)
Satisfaction (Client Satisfaction Questionnaire-8; see C10.3)	Average > 24 (or a mean score of 3 on each of the 8 items)
Intervention attendance	70% of all participants complete at the initial session and at least 2 of 3 booster sessions
Intervention Fidelity (see C8.4)	SAS and RT interventions achieve at least 80% adherence on a random subset of sessions
Safety	
Adverse events	No serious adverse events or injuries that are possibly, probably, or definitely related to study participation.
Feasibility and Acceptability—Research Procedures	
Recruitment rate	Average of 3-4 enrolled per month
STI testing procedures	80% of participants complete STI testing procedures at baseline and 70% at 6-month follow-up
Timeliness of assessments	80% of follow-up assessments occur within 3-weeks of due date
Completeness of self-report instruments and interviews	Self-report instruments have 80% of items completed and interviews 90% of items completed in 90% of cases
Retention rate	80% complete 3-mo and 70% complete 6-mo f/u assessments
Participant burden	Qualitative responses from exit interviews do not suggest undue burden of intervention or research procedures

Phase 3 (Years 1-4, October 2021 – July 2024)

General Overview

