- Participant reimbursement: Participants will have an opportunity to earn up to \$250 in total – they will receive \$50 for completing the T1: baseline assessment; \$50 for the T2: post-intervention assessment, \$25 for the exit interview; \$50 for the T3: 4-month follow up; \$50 for the T4: 6-month assessment; and a \$25 bonus if they complete all four assessments (T1-T4).
- Participants will be given the option to receive their compensation in the form of an Amazon gift card or on a VISA clincard.

Procedures

- Conduct a randomized pilot trial of STARS in 50 TW with elevated HIV risk and IPV to demonstrate the (a) feasibility, (b) acceptability, and (c) safety of the intervention.
- Examine preliminary evidence that relative to an attention and time matched control, STARS will result in improvements in our:
 - Primary outcomes;
 - Secondary outcomes; and
 - Mechanisms of change consistent with the theoretical foundations of the intervention, including greater perceived gender affirmation, and increases in empowerment and self-efficacy.
- Test, diagnose and (if positive) treat baseline STIs (and HIV) prior to initiating the STARS program. The research staff will work with participants to find gender-affirming health care clinics in their area that provide free or low-cost STI and HIV testing. Participants will be encouraged to

get tested for STIs as part of the research study; however, STI testing is not a requirement for participation.

- Complete a baseline behavioral and psychosocial baseline survey assessments administered via ACASI. Refer to the Phase 3 RCT Measures document for the complete list of standardized measures administered at baseline and at follow up.
- Upon completion of the baseline assessment, participants will be randomized to either the Intervention (STARS) condition or to a time-attention matched control (see details below).
 - **STARS Intervention** (*the final version of STARS was developed through an iterative process and refined/finalized by findings from Phases 1 and 2*)
 - Participants randomized to STARS will participate in a brief intervention immediately following the baseline (BL) assessment consisting of two one-hour sessions held one week apart and two brief 20-30 minute booster sessions held two- and four-weeks after the 2nd hour long session.
 - Participants will develop personalized risk reduction plan (RRP), which will include participants identifying “next steps” for reducing their HIV and IPV related risks.

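### For the continuous outcomes, the planned mixed model gives each randomised arm its own baseline mean, so follow-up contrasts are less precise than the collected data allow

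*SAP*

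**What the plan says.** For continuous outcomes the SAP specifies: "Linear mixed models (LMMs) with maximum likelihood estimation will be used for continuous outcomes". The examples it gives are empowerment, PTSD symptoms and depressive symptoms. The model terms are: "All models will include fixed effects for condition, time, and condition", then the interaction with time. The covariance is unstructured across time points, and the models are intention-to-treat on all available data.

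Baseline is one of the four time points: outcome means are to be "plotted across study time points (baseline, post- intervention, 4-month, and 6-month follow-ups".

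The only adjustment rule is: "Any significant baseline demographic differences will be included as covariates in the final models". The outcome's own baseline value is not listed as a covariate, and nothing sets the baseline means equal. The SAP names neither the follow-up contrast of interest nor the reference distribution for its tests.

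The protocol (section 4.2, Phase 3, Procedures) fixes the order of events: "Upon completion of the baseline assessment, participants will be randomized to either the Intervention (STARS) condition" or to the control.

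**The concern.** Because baseline is measured before allocation, any difference between the arms at baseline is chance. On the natural reading, with baseline as a response level, the condition term is a free parameter for that chance difference. Estimating it costs precision in every follow-up contrast built from the model. If baseline is left out of the response instead, its value is not used at all and precision is still lost.

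The pilot is small (up to 50 participants) and aims at 70% retention at 6 months, so precision is scarce. One affected outcome is probably primary: IPV safety is measured by the "Measure Of Victim Empowerment Related to Safety" (protocol section 4.3), which the SAP's term empowerment most likely covers. The results are to lay the ground for a larger trial.

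A secondary point is the covariate rule. Choosing demographics by baseline significance after randomisation selects on chance, not on prognostic value. No bias or inflated type I error is claimed from it.

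**Working it through.** The documents give no power, SD, alpha or correlation, so there is no stated figure to reproduce.

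**Inputs from the documents.** Up to 50 participants (protocol section 4.2, Phase 3); four time points and the model terms (SAP); retention target "80% complete 3-mo and 70% complete 6-mo f/u assessments" (protocol Table 1).

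**Assumptions.** 25 per arm; equal variances (SD = 1); two-sided alpha 0.05; 90% retained at post-intervention; the 3-month target applied to the 4-month visit; monotone dropout; correlation rho of 0.3, 0.5, 0.7 or 0.8.

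**Closed form, complete data.** Let D0 and D6 be the arm differences in means at baseline and 6 months. Any estimator D6 − b·D0 is unbiased, with variance (2/25)(1 − 2b·rho + b²).
- Change (condition-by-time contrast), b = 1: proportional to 2(1 − rho).
- Arm difference at 6 months, b = 0: proportional to 1.
- Common baseline mean, b = rho, the minimum: proportional to 1 − rho².

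The variance ratio is therefore (1 + rho)/2 against the change and 1 − rho² against the arm difference. At rho = 0.5, the change has variance 0.08 × 2 × 0.5 = 0.080 (SE 0.283), the arm difference 0.080, and the common-baseline effect 0.08 × 0.75 = 0.060 (SE 0.245). Both ratios are 0.75.

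**Four-visit model with 90/80/70% retention.** Generalised least squares with known compound-symmetric covariance, 8 mean parameters (SAP) against 7 (common baseline):

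| rho | SE change | SE arm difference | SE common baseline | ratio to change | ratio to arm difference |
|---|---|---|---|---|---|
| 0.3 | 0.376 | 0.331 | 0.320 | 0.723 | 0.934 |
| 0.5 | 0.321 | 0.321 | 0.288 | 0.806 | 0.806 |
| 0.7 | 0.251 | 0.308 | 0.236 | 0.885 | 0.586 |
| 0.8 | 0.205 | 0.300 | 0.197 | 0.924 | 0.432 |

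At rho 0.5 the difference detectable with 80% power falls from 2.80 × 0.321 = 0.90 SD to 2.80 × 0.288 = 0.81 SD. If the test is instead the 3-df interaction and the effect is constant over follow-up, the SAP model keeps 0.52, 0.67, 0.80 and 0.87 of the noncentrality at the four values of rho.

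**Covariance estimated (ML, unstructured), by simulation at the same retention.**
- Compound symmetry: 0.74, 0.83, 0.91, 0.95 against the change; 0.96, 0.83, 0.61, 0.45 against the arm difference. A separate simulation agreed within 0.02.
- AR(1), with rho between adjacent visits and so rho³ between baseline and 6 months: 0.62, 0.66, 0.76, 0.82 and 1.02, 1.01, 0.93, 0.81.

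ML and REML point estimates agreed to 4e-6 on the same data, so these ratios hold for both.

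**Type I error at nominal 5%, compound symmetry.**

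| Test | SAP model | Common baseline |
|---|---|---|
| ML, Wald: 6-month contrast | 6.6–7.5% (change), 6.0–7.3% (arm difference) | 7.3–8.3% |
| ML, Wald: 3-df | 8.9–9.7% | 10.1–10.9% |
| REML, Kenward-Roger: 6-month contrast | 4.1–6.8% | 3.7–5.5% |
| REML, Kenward-Roger: 3-df | 4.3–5.3% | 4.3–5.3% |

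**Mean 95% half-widths in SD, REML with Kenward-Roger, at the four values of rho.** Change 0.77, 0.65, 0.51, 0.42; arm difference 0.68, 0.66, 0.62, 0.61; common baseline 0.66, 0.60, 0.49, 0.41.

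**Covariate rule.** Take one demographic correlated 0.5 with the outcome, rho 0.5, same retention. The rule admits it about 5% of the time. The variance multipliers under the rule, against naming it in advance, are 1.00 vs 0.98 (change), 0.95 vs 0.80 (arm difference) and 0.985 vs 0.90 (common-baseline effect).

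**The case against.** The planned model is valid, and the study is exploratory: "We are primarily interested in exploring the pattern of results for any evidence of support". There is no power claim or efficacy threshold, so no stated conclusion falls. That stands, and it limits this to an improvement rather than an error.

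The benefit can be small or absent. Against the change, the half-width moves only from 0.51 to 0.49 at rho 0.7 and from 0.42 to 0.41 at rho 0.8. Under low, decaying correlation there is no gain over the arm difference. That also stands. But the SAP does not name its contrast, so it cannot be said to have chosen the one that loses least.

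Reported intervals might not narrow. If the SAP's ML fits were read with Wald intervals, simulated half-widths for the change are 0.71, 0.60, 0.47 and 0.39, against 0.66, 0.60, 0.49 and 0.41 after the full fix. The arithmetic is right, but those Wald intervals are too short: the corresponding tests reject more than 5% of the time. With the same inference method on both sides, the common baseline gives the shorter interval.

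The reach is narrow. Of the three primary outcomes only IPV safety could gain, and the SAP does not name its scale; empowerment might mean the mechanism-of-change measure instead. Baseline also appears in the plotting sentence, not the model sentence. Both cautions are fair. The second does not change the conclusion, since leaving baseline out of the model also wastes it.

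**Conclusion.** The concern holds as a loss of efficiency, not of validity. Under compound symmetry and the assumed retention, with the covariance estimated, a common baseline mean reduces the variance of the 6-month effect by 5–26% against the change and 4–55% against the arm difference, over rho 0.3 to 0.8. The change loses most at low rho and the arm difference at high rho. Under AR(1) the saving is 18–38% against the change and from nil to 19% against the arm difference.

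The direction is well established; the size rests on the correlation, the contrast, 25 per arm and the dropout path, all of which are assumed. The Kenward-Roger and covariate-rule figures come from one set of simulations. The Wald figures apply only if that reference distribution is used. Nothing is claimed for composite HIV risk or dichotomised IPV frequency. The covariate rule is a minor matter, nearly nil for the change contrast.

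**What to change.** For the linear mixed models:

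- Keep baseline as a response, with one common baseline mean: no condition effect at T1, and separate condition effects at T2, T3 and T4.
- Name the follow-up contrast of interest, with its visit.
- Use REML with Kenward-Roger degrees of freedom in place of ML. This should accompany the constraint, because under ML with Wald tests the constraint alone raises type I error slightly.
- Delete the baseline-significance rule. Report baseline characteristics by arm descriptively, and name any demographic covariates in advance on prognostic grounds.
- State which scale empowerment refers to, so that the analysis of IPV safety is clear.

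The same baseline constraint may be used in the logit models where they converge, without expecting a gain.

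The cost is SAP wording only. Baseline values are already collected before randomisation, so no visits, data or participants are added.
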